1 LIST OF ABBREVIATIONS AND DEFINITIONS OF TERMS

Abbreviation or Term	Definition
AE	adverse event
BMI	body mass index
BP	blood pressure
CDC	Centers for Disease Control
CMS	Centers for Medicare & Medicaid Services
COVID-19	coronavirus disease 2019
GI	gastrointestinal
HR	heart rate
IV	intravenous
LBS	Leading BioSciences (previous Sponsor name)
LB1148	investigational product - the active ingredient, TXA, is formulated in a solution containing PEG, glucose, electrolytes, and water
LOS	length of stay
mcg	microgram
mg	milligram
mITT	modified intent-to-treat
MME	Morphine milligram equivalent
NG	nasogastric tube
NPRS	Numeric Pain Rating Scale
OG	orogastric tube
PAI	Peritoneal Adhesion Index
PD	protocol deviation
PEG	polyethylene glycol
PH	proportional hazards
PBI	Palisade Bio, Inc. (Sponsor)
POI	post-operative ileus
PP	per protocol
PV	protocol violation
SAE	serious adverse event
SD	standard deviation
SOP	standard operating procedure
TXA	tranexamic acid - the active ingredient in LB1148
VRS	verbal rating score
VTE	venous thromboembolism

Abbreviation or Term	Definition
WHO	World Health Organization

2 STUDY OVERVIEW

This is a multicenter, randomized, double-blind, parallel, placebo-controlled, proof-of-concept, adaptive design, Phase 2 study to evaluate LB1148 for return of GI function, reduction of POI and intra-abdominal adhesions in subjects undergoing elective bowel resection with a planned stoma. The study is randomized to control for factors known and unknown between the treatment groups, and neither the Investigator nor the subject will know which treatment the subject will receive in order to avoid any bias in the study assessments.

This study is composed of 5 periods: Screening, Surgical, Post-Surgical, Follow-Up, and Second Surgery.

Subjects scheduled for elective bowel resection, aged 18 to 80 years inclusive, will be screened within 42 days of randomization (Study Day 1). Subjects who meet all inclusion and no exclusion criteria, and provide written informed consent, will be stratified by: 1) surgical approach (either minimally invasive technique or laparotomy) and 2) with or without a planned stoma, and then randomized to receive a split oral liquid dose of LB1148 or placebo (polyethylene glycol [PEG], glucose, and electrolytes) in a 1:1 ratio. (Note: Stratification factor #2 does not apply for subjects randomized after 01Jan2022 based on Protocol Amendment #5 updates because all subjects should have a stoma.)

All subjects will receive 350 mL of study drug (test article) 6-10 and 2-6 hours prior to surgery (Study Day 1/2). Subjects will then undergo the first surgery. Prior to surgical closure, the investigator will determine the incidence, extent, and severity of adhesions using the Intra-Abdominal Adhesion Extent and Severity Assessment Worksheet (Study Protocol, Appendix 5).

Subjects will be assessed for safety and tolerability, including AEs, physical exam, vital signs, clinical lab tests (chemistry, coagulation, and hematology) while in the hospital and on Day 30. Subjects will be monitored for return of bowel function while in the hospital and discharged following tolerance of solid food and first bowel movement.

Within 8 months of enrollment, subjects will undergo a second surgery for the purpose of ostomy takedown or other planned abdominal surgery, at which time the surgeon will determine the incidence, extent, and severity of adhesions. If a subject is not ready for the second surgery by 8 months, the investigator may consult with Medical Monitor to obtain window approval.

Unless required for safety reasons or protocol compliance, all subjects, Investigators, and study site personnel will remain blinded to the identity of the treatment from time of randomization until final database lock.

The Schedule of Assessments is provided in Appendix 1 of the protocol.

The study will evaluate the extent and severity of adhesions, as provided in the primary objective (Section 3.1), in order to determine the overall test article effect. Additionally, an evaluation of the secondary (Section 3.2) and exploratory objectives (Section 3.3) related to return of GI function, pain, and POI will be performed.

3 STUDY OBJECTIVES

3.1 Primary Objective

The primary objective of this study is to compare the change from baseline in extent and severity of intra-abdominal adhesions among subjects treated with LB1148 or placebo.

3.2 Secondary Objectives

The secondary objectives of this study are to determine the following among subjects treated with LB1148 or placebo:

- Compare time from surgical closure to resolution or appearance, as appropriate, of 1 or more of the components common to gastrointestinal (GI) dysfunction following elective bowel resection with a planned stoma.
 - Number of hours to GI2 (see Section 11.2.1 for definition)
 - Number of hours to GI3 (see Section 11.2.1 for definition)
 - Number of hours to resolution of POI
- Compare hospital length of stay (LOS, recorded in hours) through Discharge or Day 14 (whichever comes first).
- Compare the incidence of intra-abdominal adhesions at the opening of the second surgery (operationally this occurs at the time of opening)
- Compare the extent and severity of intra-abdominal adhesions at the opening the second surgery, (operationally this occurs at the time of opening)
- Compare the change from baseline in incidence, extent, and severity of intra-abdominal adhesions among subjects who had adhesions observed at the time of the first surgery
- An additional objective of this study is the evaluation of the safety and tolerability of LB1148 in subjects undergoing elective bowel resection.

3.3 Exploratory Objectives

The exploratory objectives of this study are to determine if LB1148 reduces the:

- Post-operative abdominal pain (first surgery only)
- Incidence of bowel obstruction through 30 days post-operatively (first surgery only)
- Incidence of hospital re-admittance through 30 days post-operatively (first surgery only)
- Volume of blood product transfusions needed on the day of surgery (first surgery only)

4 GENERAL METHODS

4.1 Analysis Populations

Due to coronavirus disease 2019 (COVID-19), some subjects enrolled and randomized prior to 01Jan2022 were released from the hospital prior to achieving GI2. In addition, subjects were randomized based on whether the surgery was to include a stoma or not and a subject was considered completed at Study Day 30, e.g., the second surgery was optional. Protocol Amendment 5 and 6 require subjects to have a stoma during the first surgery and require the second surgery for the subjects to be considered complete. The primary endpoint is now comparing the change from baseline in extent and severity of intra-abdominal adhesions rather than GI2 among subjects treated with LB1148 or placebo. These circumstances and changes require corresponding updates to the populations defined in the Study Protocol.

The **modified Intent-to-Treat (mITT)** population includes all randomized subjects who received any investigational test article on or after 01Jan2022, where subjects will be analyzed according to the treatment to which they were randomized.

Safety Population: The safety population will be defined as all subjects who receive any amount of investigational test article. Subjects will be analyzed according to the treatment actually received.

The **Per Protocol Population (PP)** includes subjects in the mITT population who met all inclusion and no exclusion criteria, received the complete appropriate study dose, and had no important protocol deviations or violations, where subjects will be analyzed according to the treatment to which they were randomized.

Study subjects may be replaced if found to be ineligible (violation of one or more inclusion/exclusion criteria), or if following randomization, did not go on to receive ANY amount of investigational test article.

4.2 Summarization of Data

Study results will be summarized in tabular format by treatment group, with descriptive statistics and/or in subject listings. In general, descriptive statistics for continuous variables will consist of subject count (n), mean, standard deviation (SD), minimum, first quartile, median, third quartile and maximum. Descriptive statistics for categorical variables will consist of subject counts and percentages.

All available safety and efficacy data will be included in data listings.

The efficacy analyses described in this Statistical Analysis Plan will be performed for the mITT (all efficacy endpoints) and PP Populations (primary efficacy endpoint and selected secondary efficacy endpoints), while the safety analyses will be performed for the Safety Population. All statistical tests will be 2-sided, with p-values considered nominal for this proof-of-concept study, although a p-value <0.05 will be highlighted. Unless otherwise specified, p-values will be reported to four (4) digits. No multiplicity adjustments will be performed.

4.3 Sample Size Justification and Randomization

This proof-of-concept study was originally designed to utilize an adaptive sample size re-estimation to allow for sample size adjustment based on observed data from the interim analysis. No formal knowledge of the effect size is given; therefore, no power calculations were used to assess type I and type II error rates. The goal of this study is to assess the observed effect size at the interim and adjust sample size accordingly.

Initially, subjects were randomized into an active or placebo group following a 1:1 ratio while stratified for surgery type (laparotomy or minimally invasive) and stoma (planned or unplanned). After the first 50-60 subjects were enrolled, an interim analysis was planned to assess GI2 and LOS (Discharge Order Written) endpoints. If the treatment effect size, conditional power, or reproducibility probability was deemed insufficient at the interim, then the sample size would be increased accordingly, from 120 up to 200 subjects.

The sample size justification as originally designed no longer applies to the new primary endpoint (change from baseline in extent and severity of intra-abdominal adhesions among subjects treated with LB1148 or placebo). Enrolling up to 40 subjects is estimated to provide at least 30 randomized subjects, which should be adequate to explore the feasibility of the new endpoint. The data collected from the subjects in this study will be available to power a future study using this endpoint.

Subjects randomized after 01Jan2022 were randomized by surgery type but within the planned stoma arm only.

4.4 Data Handling

4.4.1 Method for Handling Missing Data

No imputation of missing data will be performed except for times when dates are present in “time to” analyses. In those occasions, the latest or earliest time in that day will be imputed (11:59 pm or 12:01 am) to obtain the worst case (longest) for the “time to” being analyzed. (i.e., longest when the endpoint is favorable and shortest when the endpoint is unfavorable.) Time fields in the listings will not include the imputation, however, the computed “time to” fields will.

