6.4. Surgery Assessment

During surgery (where applicable), the following data should be recorded:

- The type of operation.
- The type of surgical approach (minimally invasive technique or laparotomy).

- The location of the surgical incision(s).
- Surgical time, recorded as:
 - Surgery start time, defined as the time when the initial incision is made, and
 - Surgery end time, defined as when the last suture or staple was placed.
- Ileostomy mobilization time (defined as the time from skin incision to completion of circumferential mobilization and start of preparation of ileostomy for closure).

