6.14. Hospital Discharge

Subjects may not be discharged until all of the following criteria are met:

- Passage of stool
- Ability to tolerate solid food and drink comfortably
- Adequate oral analgesia
- Subject's willingness to be discharged.

Information related to Hospital Discharge after the first bowel resection will be recorded during the Post-Surgical period as:

- When discharge order is written (date and time)
- When subject departs from the hospital (date and time)

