7.10. Recording Adverse Events

All AEs will be documented in the appropriate section of the eCRFs. Among these AEs, all SAEs (refer to [Section 7.2](#)) will be additionally documented in the SAE Report.

The following will be recorded for each event in the eCRF:

- A description of the AE in medical terms, not as reported by the subject. Whenever possible, a diagnosis should be given when signs and symptoms are due to common etiology (e.g., cough, runny nose, sneezing, sore throat, and head congestion should be reported as “upper respiratory infection”).
- The date of onset (start date).
- The date of resolution (stop date).
- The severity as assessed by the Investigator according to the definitions in [Section 7.11](#).
- The causal relationship to study drug as assessed by the Investigator; the decisive factor in the documentation is the temporal relation between the AE and the study drug (refer to [Section 7.12](#)).
- Action taken for study drug (none, study drug discontinued, study drug dose reduction, study drug delayed).
- Other action(s) taken (none, concomitant medication given, new or prolonged hospitalization, procedural surgery).
- The outcome according to the following definitions:
 - Recovered with sequelae;
 - Recovered without sequelae;
 - Ongoing, no therapy;
 - Ongoing, therapy;
 - Died, and
 - Change in toxicity grade/severity.

- SAE (as defined in [Section 7.2](#)): Yes or No.

If, in any 1 subject, the same AE occurs on several occasions (unless the AE is continuous and of stable grade), then the AE in question will be documented and assessed each time. For an SAE, the information above recorded in the eCRF will also be recorded in the SAE Report. Only AEs that fulfill the criteria for SAEs (refer to [Section 7.2](#)) should be recorded in the SAE Report.

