11.2.2 Bowel Function Endpoints

The secondary efficacy endpoints include the number of hours from surgical closure to resolution or presence, as appropriate, of:

- Achievement of GI2, defined as the toleration of solid food (subject finished a meal that required chewing and experienced no significant nausea/vomiting for four hours) and the

recovery of the upper and lower GI tract (first bowel movement; passage of stool) following surgery (the time the last skin staple or suture was placed by the surgeon)

- Nausea with a Verbal Rating Score (VRS) ≥ 3 (moderate to severe) (Listing only)
- Vomiting or retching* (Listing only)
- Presence of flatus (Listing only)
- Bowel movement (presence of stool from anus or ostomy)
- Insertion and reinsertion of nasogastric (NG)/orogastric (OG) tube*
 - Removal of NG/OG tube* (Listing only)
- Ability to tolerate a liquid oral diet (liquid diet ordered, and subject is able to sustain oral liquid intake without need for IV fluid administration for hydration)
- Ability to tolerate a solid oral diet (solid food ingestion without significant nausea/vomiting for four hours)
- Achievement of GI3, identical to GI2 except recovery of the upper and lower GI tract is defined by either bowel movement or flatus
- Resolution of POI, defined as having resolved when all of the following criteria are met:
 - Absence of nausea AND vomiting for 12 hours without a NG/OG tube
 - Ability to tolerate a solid or liquid oral diet
 - Passage of flatus OR stool over the preceding 24 hours

The following POI parameters will also be evaluated:

- Incidence of POI (Within 14 days of first surgery, After Discharge), defined as the greater than expected inability to tolerate liquids or solids during the post-operative period
 - Within 14 days of first surgery subjects will be identified by AE preferred term (PT) **and** by a confirmatory imaging study within the start/stop dates of the POI
 - The AE PTs are ileus, post-operative ileus, small bowel obstruction, bowel obstruction, partial bowel obstruction, mechanical bowel obstruction, and non-mechanical bowel obstruction
- Incidence of POI after hospital discharge
 - Subjects will be identified by AE PT as listed above

*Vomiting and retching, as well as insertion, reinsertion, and removal of NG/OG tube will be treated as binary (yes/no) variables.

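### SAP 4.4.1 sets no upper bound on an imputed clock time, so a date-only recovery event on the discharge day is timed after the subject left hospital

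*SAP*

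**What the plan says.** **The rule.** SAP 4.4.1 is narrow in scope: "No imputation of missing data will be performed except for times when dates are present in" time-to-event analyses. There, "the latest or earliest time in that day will be imputed (11:59 pm or 12:01 am) to obtain the worst case (longest"), and the direction is "longest when the endpoint is favorable and shortest when the endpoint is unfavorable". A favorable event with only a date gets 11:59 pm; an unfavorable one gets 12:01 am. The derived durations carry the imputed value, while the time fields in the listings do not. The section does not tie the imputed time to any other recorded time. The censoring table in SAP 11.4 gives only Study Day 14.

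**The clock.** SAP 11.2.2 sets the origin: "The secondary efficacy endpoints include the number of hours from surgical closure to resolution or presence, as appropriate, of" the listed events. Protocol 6.4 records that origin as "Surgery end time, defined as when the last suture or staple was placed".

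**Discharge.** Protocol 6.14 states: "Subjects may not be discharged until all of the following criteria are met". Stool and tolerance of solid food are among those criteria. The same section records "When discharge order is written (date and time") and, as a separate item, the date and time of departure. Protocol 6.13 collects GI function daily until it returns or the subject is discharged, and the schedule in Appendix 1 has no GI rows after the discharge visit.

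**Use of the times.** In SAP 11.5, GI2 and GI3 have Cox and Kaplan-Meier analyses in both mITT and PP. Bowel movement and solid diet have both analyses in mITT. Discharge order and actual discharge have both analyses in both populations.

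**The concern.** A worst-case convention should return the worst value that the data allow. Here it can return a value that the data rule out. If a subject's first stool is dated on the discharge day without a clock time, the protocol says that it happened before departure, and the departure time is in the database. The rule nevertheless puts the stool at 11:59 pm that night.

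The same subject could then show GI2 later than actual discharge, with both variables measured from surgical closure and both modelled. Time to GI2 also feeds the scatter-plot matrix in SAP 10. Recovery on the discharge day is a plausible case, because subjects leave once they tolerate solid food and have had a bowel movement.

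What is at stake is the internal consistency of the bowel-function and length-of-stay results, plus some avoidable noise in a small study. The primary comparison is not at stake.

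**Working it through.** The SAP gives no figure that depends on this rule, so there is none to reproduce. The check is clock arithmetic.

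**Inputs**
- Imputed time for a favorable event: 23:59 on the event date (SAP 4.4.1).
- Origin: surgical closure (SAP 11.2.2).
- Upper bound available: departure date and time (Protocol 6.14).
- Assumed, because the documents give no clock times: closure at 14:00 on Day 0; departure on Day 5 at 09:00, 12:00, 16:00 or 20:00; event dated Day 5 with no time.

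**Formulas**
- Imputed duration = 5 × 24 h + (23:59 − 14:00) = 120 + 9.98 = 129.98 h.
- Duration to departure = 120 h + (departure time − 14:00).
- Excess = 23:59 − departure time. The closure time cancels.

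| Departure, Day 5 | Closure to departure (h) | Imputed event (h) | Excess (h) | With cap at departure (h) |
|---|---|---|---|---|
| 09:00 | 115 | 129.98 | 14.98 | 115 |
| 12:00 | 118 | 129.98 | 11.98 | 118 |
| 16:00 | 122 | 129.98 | 7.98 | 122 |
| 20:00 | 126 | 129.98 | 3.98 | 126 |

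The excess is positive for any recorded departure before 11:59 pm. If the departure time is itself missing and imputed to 11:59 pm, the two times coincide and there is no contradiction.

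**Which endpoints.** GI2 needs both solid food and stool, so one date-only component on the discharge day is enough to move it. GI3 behaves the same way. A discharge order with a date but no time would also be placed after a recorded departure.

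**Scale for one subject.** SAP 4.3 expects at least 30 randomized subjects at 1:1. Assuming 15 per arm, all in mITT, one affected subject shifts an arm's mean time by between 3.98 / 15 = 0.27 h and 14.98 / 15 = 1.00 h. This is an effect per affected subject. The total cannot be estimated without the number of date-only events on discharge days.

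**Lower end.** An unfavorable event dated Day 0 without a time gets 00:01. With closure at 14:00 that is 00:01 − 14:00 = −13.98 h; closures from 09:00 to 20:00 give −8.98 h to −19.98 h. The rule has no floor either, but this case has almost no route into a model, as explained under the objection.

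**The case against.** The strongest reply is that the rule is prespecified, deliberately conservative and identical in both arms. A late discharge-day time is still a valid positive event time, because censoring is at Study Day 14 and not at discharge. No record is lost, and nothing suggests a direction of bias between arms. Protocol 6.13 also asks for date and time of stool, first flatus and solid food, so missing times may be few. All of this stands and keeps the point small. It does not make the imputed value possible.

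Three stronger readings are tempting, and the documents do not support them.

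- **Adverse events on Day 0 are timed before the operation, and subjects drop out of the models.** The rule covers only time-to-event variables, and SAP 12.1 tabulates adverse events by frequency. Nausea and vomiting are listing only, NG/OG use is binary or listing only, and GI assessment starts on post-operative Day 1. The one possible route is postoperative ileus. Protocol 7.10 lists "The date of onset (start date") without a clock time, but Protocol 6.13 asks for date and time of an in-hospital ileus event. The ileus duration in SAP 11.2.2 is time to resolution, a favorable event. Only the ileus row in SAP 11.5, if read as onset, could go negative. That would need an onset dated Day 0 with a missing time, for a condition defined as lasting longer than expected after surgery.
- **The missing cap inflates mean times by the missing rate times an average shift.** The documents give no missing rate. Such a product would also measure the whole worst-case convention on every date, whereas a cap changes only discharge-day events.
- **A missing closure time would start the clock before the operation.** Surgery end time is a specified item, and nothing suggests that it would be absent.

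**Conclusion.** The point holds as a narrow drafting defect. SAP 4.4.1 puts no upper bound on an imputed favorable time, so a date-only GI2, GI3, bowel movement or solid-diet event on the discharge day falls after the recorded departure. The excess is about 4 to 15 h for assumed departures from 20:00 back to 09:00. That contradicts the discharge criteria and the in-hospital collection of GI data.

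The conclusion rests on the clock time being missing, the departure time being recorded and the discharge criteria being followed. SAP 4.1 reports releases before GI2 among subjects randomized before 01Jan2022, but those subjects are outside the mITT population. Even where the criteria were not followed, a recovery event collected in hospital still precedes departure.

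The impact is limited to secondary and exploratory time-to-event endpoints, all with nominal p-values. The primary adhesion scores involve no clock time and are untouched.

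**What to change.** Add to SAP 4.4.1:

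> An imputed time for a favorable in-hospital event will be no later than the recorded hospital departure date/time. As a safeguard, no imputed event time will be earlier than surgical closure, and an event time equal to closure will be set to a small positive value (e.g., 1 minute).

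The cap belongs at departure, not at the discharge order. Protocol 6.14 records the two separately and its criteria govern discharge itself, so an order written earlier that day need not follow stool or solid food. The capped value is still the worst case, but now a possible one. The floor is there for completeness.

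The cost is this short SAP addition and a minimum and maximum in the derivation program. No new data are needed, and the change can be made before database lock without reference to treatment assignment.
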